##### **Rationale and Background**

The European Medicines Agency (EMA) Pharmacovigilance Risk Assessment Committee (PRAC) recommended in the Article 107i procedure according to Directive 2001/83/EC for HES-containing medicinal products (EMA/H/A-107i/1376) in October 2013 that HES solutions must no longer be used to treat patients with sepsis or burn injuries or critically ill patients because of an increased risk of kidney injury and mortality while the benefit-risk ratio for HES-containing medicinal products remains favourable in the treatment of hypovolaemia due to acute blood loss when crystalloids alone are not considered sufficient.

The final implementing decision, issued by the European Commission (EC) on December 19, 2013, implicates new contraindications, new special warnings and precautions for use as well as other changes to the European Product Information (PI) [Summary of Product Characteristics (SmPCs); Package Leaflet] for risk minimisation measures (as requested in Annex III of this EC decision).

To “evaluate the effectiveness of the risk minimisation measures taken” (as requested in Annex IV of the EC decision), the concerned MAHs of HES products subject to the PRAC procedure were asked to conduct a Drug Utilisation Study (DUS) with HES-containing medicinal products in several European Union (EU) Member States.

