## 7. Rationale and Background

Following the publication of investigator initiated clinical trials such as 6S (Perner et al. 2012), CHEST (Myburgh et al. 2012) and VISEP (Brunkhorst et al. 2008), comparing HES-containing solutions with crystalloids in critically ill patients (e.g. septic patients), the EMA, initiated procedures to assess the benefits and risks of HES-containing solutions, especially in critically ill patients.

In the relevant European referral procedure according to Article 107i of Directive 2001/83/EC for HES-containing medicinal product (EMEA/H/A-107i/1376) the PRAC, recommended in October 2013 that HES-solutions must no longer be used to treat patients with sepsis or burn injuries or critically ill patients because of an increased risk of kidney injury and mortality in these patients but that the benefit-risk ratio for HES-containing

medicinal products remains favourable in the treatment of hypovolaemia due to acute blood loss when crystalloids alone are not considered sufficient.

This recommendation was adopted by majority vote by the Coordination Group for Mutual Recognition and Decentralised Procedures human (CMDh). The final implementing decision was issued by the EC on December 19, 2013 by which this referral procedure was positively concluded. This implicates new contraindications, special warnings and precautions for use as well as other changes to the European PI for risk minimisation measures (as requested in Annex III of the EC decision).

In addition, the concerned MAHs were requested to conduct a DUS with HES-containing medicinal products in several EU Member States to “evaluate the effectiveness of the risk minimisation measures taken” (as requested in Annex IV of the EC decision).

The DUS will be performed by the MAH Fresenius Kabi Deutschland GmbH and will include all available HES-containing medicinal products of this MAH in those European countries where the DUS will be performed. A detailed overview about the concerned medicinal products in the individual country is provided in Annex 1a.

In summary, the scope of this DUS is to investigate the adherence of hospital physicians to the revised European PI for HES-containing medicinal products during routine administration of HES-solutions in hospitals to evaluate the effectiveness of the risk minimisation measures taken.

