## **8. Research Question and Objectives**

The objective of the DUS is to assess the adherence of hospital physicians to the revised European PI for HES-containing medicinal products concerning indication, posology (dosage), and contraindications (as listed in Annex III of the EC decision).

In general, due to its retrospective and non-interventional nature the DUS can only be used to generate hypotheses and not to test any a-priori specified hypothesis.

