## **9. Research Methods**

### **9.1 Study Design**

The study is a retrospective, non-interventional, multinational, multi-centre European DUS of use of HES-containing medicinal products in hospitals. The DUS will follow national laws and regulations.

Outcome measure is the adherence to the concerned sections of the revised European PI for HES-containing medicinal products.

Usage of these medicinal products according to indications, posology (dosage), and contraindications as specified in the revised PI of the HES solutions will be assessed.

In the DUS, routine clinical use of HES-containing medicinal products of Fresenius Kabi will be documented by retrospective data collection from patient charts within a predefined timeframe. Retrospective data collection best reflects actual patterns of use and allows reducing bias as described in [Section 9.9](#) to a minimum. To ensure that there is a very high coverage of patients administered HES containing products, site selection will focus on sites using electronic PDMS. Patient charts will be thoroughly searched via free text, ICD-10 code (diagnosis), and ATC code (medication) to ensure identification of eligible patients as complete as possible.

Following the final approval of the submitted protocol by the PRAC, notification to NCAs and positive IEC opinion as required by national and local regulations and requirements, as well as the administrative processes such as site selection and contracting of sites will be initiated.

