##### **Basic Assessment**

- Hospital (name, address)
  
- Patient admission date (calendar week, year)

- Ward(s) where HES of Fresenius Kabi was administered
  - ICU (if various, specify)/PICU/Operating room/Surgical ward/Intermediate care/Emergency unit/Burns unit/Other
- Demographic data
  - Age (< 18 years or ≥ 18 years)
  - Weight
- Main diagnosis at hospital admission (ICD-10 code plus corresponding plain diagnosis text)
- Indication for HES use
  - Treatment of Hypovolaemia due to acute blood loss (yes/no)
  - Treatment of Hypovolaemia without acute blood loss (yes/no)
  - HES used exclusively for “Prophylaxis of Hypovolaemia” and not for “Treatment of Hypovolaemia” (yes/no)
  - Other (yes/no; if yes ICD-10 code)

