### **9.6.2 Patient Data Anonymisation**

Patient data investigated will be de-identified in an unlinked manner to personal identifier. The documented data are restricted to personal identifier, patient age range (< 18 years or ≥ 18 years), medical procedures, diagnostic codes according to ICD-10, and name, dose, and duration of supply of prescribed HES product (and other drugs, if applicable). The full list of anonymised patient specific variables is specified in [Section 9.3.2](#).

Fresenius Kabi will in no way be able to backtrace the identification of any study subject.

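### No listed variable records the crystalloid condition attached to the retained HES indication, so adherence on indication cannot be fully assessed and can only be over-stated on this account

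*Protocol*

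**What the plan says.** The Abstract of the Protocol (Rationale and Background) reports the referral conclusion that the benefit-risk balance stays positive for "treatment of hypovolaemia due to acute blood loss when crystalloids alone are not considered sufficient". Section 7 repeats this in the same terms and says that the resulting decision changed the product information.

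Section 8 sets the objective as adherence to the revised product information "concerning indication, posology (dosage), and contraindications (as listed in Annex III of the EC decision". Section 9.1 adds: "Outcome measure is the adherence to the concerned sections of the revised European PI for HES-containing medicinal products".

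The indication block in Section 9.3.2 (Basic Assessment) has four items:
- "Treatment of Hypovolaemia due to acute blood loss (yes/no"
- "Treatment of Hypovolaemia without acute blood loss (yes/no"
- exclusive prophylactic use
- other, with a diagnosis code

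The rest of Section 9.3.2 covers ward, age group, weight, admission diagnosis, co-morbidities, HES given before admission, HES given at the site (product, amount and times per bag) and discharge from the ward.

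Section 9.6.2 refers to Section 9.3.2 for the full list of patient variables. It also describes the data as including "name, dose, and duration of supply of prescribed HES product (and other drugs, if applicable", but no other drug or fluid appears in Section 9.3.2.

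Section 9.7.2 says that the retrospective design will reveal both in-label and off-label use. The limitations in Section 9.9 do not mention the crystalloid condition.

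**The concern.** The retained use is described with two conditions: the hypovolaemia is due to acute blood loss, and crystalloids alone are not judged enough. The data set can test only the first. A patient treated for blood-loss hypovolaemia looks the same in the data whether or not the second condition was met.

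Indication is one of the three areas in which adherence is to be measured, and the study exists to judge whether the risk minimisation measures worked. Leaving out a required condition moves patients one way only, from non-adherent to apparently adherent, so the error favours a conclusion that the measures were effective.

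A statistical analysis plan can define how collected data are classified, but it cannot supply a variable that was never abstracted. Later repair is also doubtful. Section 9.6.2 has the data de-identified without a link to the patient, and Section 9.9 says that the CRO cannot check entries against the original records.

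**Working it through.** **Step 1. Conditions set against variables.**

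| Part of the retained use (Abstract; Section 7) | Variable in Section 9.3.2 |
|---|---|
| Treatment of hypovolaemia, not prophylaxis | Yes, separate item |
| Cause is acute blood loss | Yes, separate items with and without blood loss |
| Crystalloids alone not considered sufficient | None |

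The co-morbidity and HES administration blocks add no other fluid, and the mention of other drugs in Section 9.6.2 has no matching field. No combination of listed variables can stand in for the third row.

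**Step 2. The plan's own precision figures.** Section 9.5 gives exact 95 % intervals at a 3 % non-compliance rate. The limits are the 0.025 quantile of Beta(x, n − x + 1) and the 0.975 quantile of Beta(x + 1, n − x).
- n = 334, x = 10: 1.44–5.44 % (plan: 1.4–5.4 %).
- n = 3000, x = 90: 2.42–3.67 % (plan: 2.4–3.7 %).

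Both reproduce. The sample-size arithmetic is not in dispute.

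**Step 3. What the missing condition does to the estimate.** Let p be recorded non-adherence and f the share of patients recorded as adherent who did not meet the crystalloid condition. Then

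true non-adherence = p + (1 − p) × f, and the shortfall = (1 − p) × f.

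The shortfall is never negative and does not contain n, so more patients or sites do not reduce it.

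**Step 4. Scale.** The documents give no value for f. With p = 3 % from Section 9.5, the value of f at which the true rate reaches the upper planned limit is:
- overall: (3.7 − 3.0) / 97 = 0.0072, about 0.7 %;
- per country: (5.4 − 3.0) / 97 = 0.0247, about 2.5 %.

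For assumed values of f, purely as illustration:

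| f (assumed) | True rate if 3 % is recorded |
|---|---|
| 1 % | 0.03 + 0.97 × 0.01 = 3.97 % |
| 5 % | 0.03 + 0.97 × 0.05 = 7.85 % |
| 10 % | 0.03 + 0.97 × 0.10 = 12.7 % |
| 20 % | 0.03 + 0.97 × 0.20 = 22.4 % |

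These lines show how sensitive the result is to f. They do not estimate the bias in this study.

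**The case against.** Several counter-arguments have force.

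- **The label text is not in the document at hand.** The standard for adherence is Annex III of the EC decision. The Abstract and Section 7 report the referral's benefit-risk conclusion. That the revised indication carries the crystalloid condition is a reasonable inference, since the Protocol presents the label change as following from that conclusion, but it is not a quotation of the label.
- **No adherence rule is written down.** That such patients would be counted as on-label on indication is therefore also an inference. It stands because nothing in Section 9.3.2 could classify them otherwise on indication.
- **The eCRF may hold more than Section 9.3.2.** Section 11 says that off-label use, misuse and medication error will be documented and coded, and Section 9.3.2 has no such fields. This weakens the argument from the list alone. But Section 11 names no crystalloid information, and a general off-label entry would still need a source for that judgement.
- **The study is descriptive and hypothesis-generating.** Dose, contraindications and the other indication categories remain measurable. This limits the consequence but does not close the gap.

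Two stronger readings are tempting and are not supported. A reader might infer that any first-line use of HES is off-label and is being missed. The wording refers to what is considered sufficient, which is a prescriber's judgement, and it does not say that crystalloids must be given first. A reader might also assume a blood-loss share, say 70 %, and an f of 5–20 %, obtain 0.70 × 5 % = 3.5 to 0.70 × 20 % = 14 missed points, and set these against the 1–4 % rates in Section 9.5. The two do not fit together. If blood loss is the only on-label category, a 70 % share already means about 30 % recorded non-adherence on indication, because the existing items separate the rest.

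**Conclusion.** The point holds in this form: the crystalloid condition cannot be assessed from the listed variables, the gap is not disclosed, and Section 9.7.2 claims more than the data can show. On this account alone, measured non-adherence on indication is a lower bound and measured adherence an upper bound. Other errors of abstraction could act in either direction.

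The direction is firm and the size is unknown. The break-even values of about 0.7 % overall and 2.5 % per country show only that a small failure rate would exceed the precision for which the study was sized.

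The conclusion assumes that the revised indication contains the condition as the Abstract and Section 7 describe it, and that Section 9.3.2 is complete, as Section 9.6.2 says. The break-even values further assume recorded non-adherence of 3 %, with f applied to the patients recorded as adherent.

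**What to change.** Before abstraction starts, add two items to Section 9.3.2:

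1. Charted statement that crystalloids alone were insufficient: yes / no / not documented.
2. Crystalloid given before or with the first HES bag: yes / no / not documented.

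The first addresses the condition. The second is a supporting proxy only: crystalloid given does not show that it was judged insufficient, and crystalloid not given does not show that it would have been judged sufficient. It should not decide adherence by itself.

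Report indication adherence twice, for blood loss alone and for blood loss with the documented crystalloid condition. Show the not-documented share separately in each country and overall.

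If the items are not collected, say in Sections 8, 9.1 and 9.7.2 that the crystalloid condition is not assessed and that indication adherence is therefore an upper bound, and list this in Section 9.9. In either case, reconcile the mention of other drugs in Section 9.6.2 with the variable list.

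The cost is slightly longer abstraction, from charts that sites already search for the volume and times of each HES bag. Some entries will be not documented. How many is unknown, and a high share would itself limit what can be concluded about the condition. The change concerns data collection and reporting only.

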#### **HES Administration in the Hospital (DUS Study Site)**

- Trade name of prescribed HES product
- Posology (Dosage)
  - HES infusion (first to last bag/bottle)
    - Start of infusion (Day Y/Time hh:mm) of each bag/bottle
    - Amount infused (ml) of each bag/bottle
    - End of infusion (Day Z/Time hh:mm) of each bag/bottle

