### **9.7.2 Validity of Outcome Measures**

Assessing adherence to the PI specifications in a non-interventional and retrospective DUS will reduce bias to a minimum. In contrast to a prospective setting, the retrospective design of the DUS will not influence the clinical practice but will discover any in-label as well as off-label use.

The inclusion of several countries, study sites and the requirement of inclusion of all identified, HES-treated patients with products of Fresenius Kabi within a predefined timeframe, as well as the dedicated data acquisition in this DUS preferably by electronic PDMS, should provide a comprehensive record of HES-containing medicinal products used in routine clinical practice over all involved investigational sites.

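### The prophylaxis item records only exclusive prophylaxis, so prophylactic HES in a patient also treated for acute blood loss is lost from the indication items

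*Protocol*

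**What the plan says.** Adherence on indication is one of the three components of the outcome (protocol Sections 8 and 9.1), next to dosing and contraindications. Section 9.7.1 counts patients whose use does not adhere to the revised product information, with percentages and 95 % confidence intervals.

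The indication items stand in Section 9.3.2, Basic Assessment, one set per patient:

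- The first item covers treatment after bleeding: "Treatment of Hypovolaemia due to acute blood loss (yes/no".
- The second item covers treatment in the absence of bleeding: "Treatment of Hypovolaemia without acute blood loss (yes/no".
- The third item covers prophylaxis: "HES used exclusively for “Prophylaxis of Hypovolaemia” and not for “Treatment of Hypovolaemia” (yes/no".
- The fourth item takes whatever remains: "Other (yes/no; if yes ICD-10 code".

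Only the third is conditional on the answers to others. Later in Section 9.3.2, the in-hospital administration fields are collected bag by bag, for example "Start of infusion (Day Y/Time hh:mm) of each bag/bottle", together with the amount and the end time. No indication is attached to a bag.

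On the label itself, the abstract and Section 7 say that the benefit-risk ratio "remains favourable in the treatment of hypovolaemia due to acute blood loss when crystalloids alone are not considered sufficient". Annex III of the EC decision, against which adherence is judged, is cited but not reproduced in the text at hand. Section 9.7.2 says that the retrospective design "will discover any in-label as well as off-label use". Section 11 says that off-label use will be documented in the eCRF and coded.

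**The concern.** HES may be started before bleeding and continued after it within one hospital stay; the protocol lists the operating room and the surgical ward among the places of use. With the exclusive wording, any treatment use forces the prophylaxis item to 'no', so the prophylactic part of such a course leaves no trace in the indication items. Treatment without blood loss has no such condition and stays visible beside treatment for blood loss. The protocol gives no reason for the difference.

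The study exists to evaluate risk minimisation measures. An item that can hide one kind of departure from the indication, and cannot create a false one, pushes reported adherence on indication in the favourable direction. No rule in a later analysis plan can recover from the listed fields what they do not hold.

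**Working it through.** **Step 1. What each course of HES produces on the form.** The item wordings in Section 9.3.2 are applied literally, with 'Other' left at 'no'.

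| Use in the patient | Due to acute blood loss | Without acute blood loss | Exclusively prophylaxis |
|---|---|---|---|
| A. Blood loss only | yes | no | no |
| B. Prophylaxis only | no | no | yes |
| C. Prophylaxis and blood loss | yes | no | no |
| D. Prophylaxis and treatment without blood loss | no | yes | no |
| E. Blood loss and treatment without blood loss | yes | yes | no |

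Rows A and C are identical. Rows B, D and E all differ from A, so some use outside blood-loss treatment remains visible in each. The loss of information is confined to row C.

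**Step 2. Can another field separate A from C?** The bag-level fields give start, amount and end, which do not identify why a bag was given. 'Other' requires an ICD-10 code, and no instruction sends mixed prophylaxis there. Section 11 commits to documenting off-label use in the eCRF, but Section 9.3.2 lists no field for it.

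**Step 3. Direction.** Let m be the share of all patients in row C, with no other indication item flagged. If prophylaxis is outside the indication and any such use counts:

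indication non-adherence = recorded indication non-adherence + m, with m ≥ 0.

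The recorded figure is too low by m and cannot be too high for this reason. For a combined measure (any deviation on indication, dosing or contraindications) the shortfall is at most m, because some row C patients will be counted for another deviation.

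**Step 4. The plan's own precision, as a yardstick.** Section 9.5, Table 1, reproduces with the exact binomial interval:

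- N = 334 at 3 %: 10 events, 1.4 % to 5.4 %, as printed.
- N = 3000 at 3 %: 90 events, 2.4 % to 3.7 %, as printed.

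All 32 cells of the table reproduce to one decimal. These intervals cover sampling error only. If 3 % were recorded, the rate including row C would pass the printed upper limit once m exceeds

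- 5.4 − 3.0 = 2.4 percentage points in a country of 334,
- 3.7 − 3.0 = 0.7 percentage points in the total of 3000.

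**Step 5. Patients concerned, by assumption.** The document gives no value for m. Purely as an assumed range, 1 %, 2 %, 5 % and 10 % of 334 are 3.3, 6.7, 16.7 and 33.4 patients per country. Nothing in the document says where in this range, or outside it, the true share lies.

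**The case against.** The case on the other side has several parts.

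- *Other routes exist.* A site could tick 'Other' for the prophylactic part, and Section 11 promises that off-label use will be documented. The eCRF manual listed in Section 9.8.1 is not at hand and might give the instruction. This stands as a reason for moderate confidence. It does not close the gap, since no listed field or instruction in the protocol directs mixed use to either place.
- *The label text is not shown.* The abstract and Section 7 summarise a benefit-risk conclusion, not the indication wording. That prophylaxis before blood-loss treatment is a deviation is an inference, supported by the form's own separation of prophylaxis from treatment. The point is conditional on it.
- *Section 9.7.2 is about something else.* Its sentence on discovering off-label use contrasts retrospective with prospective observation. It is at most loosely worded, and the point does not need it.
- *A patient-level indication is a legitimate choice* for chart abstraction, and nothing shows that charts state a reason for each bag. This stands; the patient-level item only needs different wording.

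Three stronger readings are tempting. A reader might infer that the mixed patient is scored as fully on-label. No scoring rule is printed, and the same patient can still fail on dosing or contraindications. A reader might infer that all mixed courses become adherent; only row C does. A reader might also add an assumed share of 10 % to the 3 % of Section 9.5 and conclude that a reported 3 % conceals 13 %. The 3 % is an example chosen to show interval width, the share has no source in the document, and the sum assumes no overlap with other deviations.

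**Conclusion.** The point holds in a limited form. On the listed indication items, a patient with prophylactic HES and treatment for acute blood loss cannot be told apart from one treated for blood loss only. Provided that prophylaxis lies outside the revised indication, non-adherence on indication can only be understated for this group.

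The size is unknown. The thresholds of 2.4 points per country and 0.7 points overall show only how small a share would matter against the planned precision at the illustrative rate; they are not estimates of the bias. The conclusion rests on the literal wording of the items, on the reading of the label from the rationale, and on the absence of a listed field or instruction for mixed use.

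It should be fixed, with moderate confidence. The one-sided direction and the low cost argue for the change; the unknown frequency and the eCRF manual not at hand argue against calling it indispensable.

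**What to change.** Replace the exclusive wording by an item asking whether any HES was given for prophylaxis of hypovolaemia (yes/no), answered independently of the treatment items. Exclusive prophylaxis can then be derived as 'yes' on this item with 'no' on both treatment items, so nothing now collected is lost.

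State in the protocol that a patient with any use outside the label indication counts as non-adherent on indication, and report exclusive and mixed prophylaxis separately so that both readings are open to the assessor. Say in the eCRF manual how mixed use is entered, and how the Section 11 commitment on off-label use is met by a field. Recording the indication per bag is optional, where charts contain it.

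The cost is one reworded item, a line in the manual, slightly more abstraction work, and possibly a lower reported adherence. The sample size and the planned descriptive analysis do not change.
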